Participants presenting to the Atlanticare Pain Management clinic received a lidocaine injection after dry needling into the location of the MTP by a board-certified pain management physician. First, the upper trapezius MTP was identified and isolated. After application of a coolant to numb the area, the isolated trigger point was penetrated using a 30-gauge needle, to a depth adjusted depending on the patient, into the subcutaneous tissue. The duration of treatment was approximately 1-2 minutes. Once the myofascial tension was relieved, 2 mL of 0.5% lidocaine was injected into the MTP.

After their respective interventions, the patient completed an immediate post-intervention survey, consisting of a 0-10 pain scale. Finally, approximately 7-10 days after the intervention, patients were contacted by telephone to complete the one-week post-intervention survey consisting of a 0-10 pain scale.

Outcome Measures

Pain intensity; measured using a point system; where 0 = no pain and 10 = maximum pain. Although this is a subjective measurement by the patient, we are interested in looking at the difference between pre- and post-intervention pain intensity ratings.

Data Analysis

The data was analyzed using R software. Values of interest include mean, median, standard deviation, normal distribution, confidence intervals etc. Intergroup and intra-group comparisons were conducted using independent t-tests and paired t-tests, respectively. Alpha level is set at 0.05 and p values less than that will be considered statistically significant. A descriptive analysis of the outcome variables was conducted to compare between the intervention groups. The homogeneity of sociodemographic data (age, sex, comorbid conditions) and outcome measures were analyzed using the Fischer test and Pearson chi square test, respectively.

The outcome measures were analyzed separately in both treatment groups. The contrast between the treatment groups was analyzed. A univariate analysis of the difference of the outcome variables at the different time points (before the intervention, immediately after the intervention, and a week post the intervention) were obtained through the student *t*-tests. A multivariate analysis was carried out using multiple logistic regression models with age, sex, and intervention group (Injection = 0, OMM = 1) factored as the independent variables.

Results

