The study was completed at two primary locations. There were a total of 10 eligible participants from the lidocaine treatment group and 21 eligible participants from the OMM treatment group enrolled after screening for the inclusion and exclusion criteria. 1 subject from the lidocaine treatment group was lost during follow-up at one week post intervention and thus excluded from the per protocol analysis of the study. The remaining participants' data were analyzed in SPSS 26. No significant difference was found between the two groups in regard to sociodemographic data (Table 1). At baseline, the OMM group had a mean pain intensity level of 2.76 (SD 1.8) while the lidocaine treatment group had a mean pain intensity level of 7 (SD 2.8). Descriptive statistics of pain intensity between the two groups demonstrate considerable variance (Table 2).

Within the OMM group, an independent samples t-test found a statistically significant difference between the pre-intervention and immediate post-intervention pain levels, $t(20) = 2.10, p = .048$. The mean pre-intervention pain level ($M = 2.76, SD = 1.84$) was significantly higher than the immediate post intervention pain level ($M = 1.86, SD = 0.96$). An independent samples t-test found a statistically significant difference between pre-intervention and one-week post-intervention pain levels, $t(20) = 2.68 p = .014$. The mean pre-intervention level of pain ($M = 2.76, SD = 1.84$) was significantly higher than one-week post-intervention ($M = 1.81, SD = 2.01$).

Within the lidocaine group, an independent samples t-test did not demonstrate a statistically significant difference between pre-intervention and immediate post-intervention pain levels, $t(20) = 1.17, p = 0.27$. The mean pain level pre-intervention ($M = 7, SD = 2.87$) was higher than immediately post-intervention ($M = 6.60, SD = 2.32$). When evaluating the difference in level of pain from pre-intervention to one-week post-intervention, an independent samples t-test was not statistically significant, $t(20) = 2.16 p = .062$. The mean level of pain pre-intervention ($M = 7, SD = 2.87$) was higher than one-week post-intervention ($M = 4, SD = 2.18$). Pain intensity between the two groups are also demonstrated graphically in Figure 1, with time point one corresponding to pre-intervention, two corresponding to immediately post-intervention and three corresponding to 1 week post intervention.

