To investigate the treatment effect between groups across time, a mixed design two factor ANOVA was utilized. As expected, due to small sample size, heterogeneity of covariance matrices was detected. This is considered a limitation of the study. Also, since a repeated measures design was implemented across three time periods, Mauchly's test of sphericity was examined and found to be significant ($p = .042$). This indicates that sphericity cannot be assumed, so a Greenhouse-Geisser statistic was computed. A statistically significant interaction effect was detected, $F(1.65, 56) = 3.90, p = .034$. Due to p-value being less than 0.05, we can confidently reject the null hypothesis and accept the alternative hypothesis.

[figure not shown]
Table 1.

Sociodemographic Data	Mean (SD) or Number (%)		P value
	OMM (n = 21)	Lidocaine (n = 10)	
Sex (%), n = 31 (100%)	21 (100)	10 (100)	
Male, n = 7 (22.6%)	5 (23.8)	2 (20)	
Female, n = 24 (77.4%)	16 (76.2)	8 (80)	
Age, y			
Subjects from 20 – 29 y, n = 22 (71%)	21 (100)	1 (10)	
Subjects from 30 – 39 y, n = 1 (3.2%)	0	1 (10)	
Subjects > 60y, n = 8 (25.8%)	0	8 (80)	
Ethnicity			
Caucasian, n = 20 (64.5%)	11 (52.4)	9 (90)	
African American, n = 1 (3.2%)	1 (4.8)	0	
Latino or Hispanic, n = 4 (12.9%)	3 (14.3)	1 (10)	
Asian, n = 6 (19.4%)	6 (28.6)	0	
Pain Intensity			
Pre-intervention	2.76 (1.8)	7 (2.8)	
Post-intervention (immediate)	1.86 (0.9)	6.6 (2.3)	0.026
Post-intervention (one week)	1.81 (2.0)	4 (2.2)	0.062

Table 2.

	Group	Mean	Std. Deviation	N
Pre-intervention Pain	OMM	2.76	1.84	21
	Lidocaine	7.00	3.04	9
	Total	4.03	2.96	30
Post-intervention immediate pain	OMM	1.86	0.96	21
	Lidocaine	6.56	2.45	9
	Total	3.27	2.66	30
Post-intervention 1 week pain	OMM	1.81	2.01	21
	Lidocaine	4.00	2.17	9
	Total	2.47	2.27	30

Figure 1.

Discussion

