We specifically note that this is a suitable treatment modality for all physicians, both osteopathic and allopathic, as we merge our skill sets over time in a unified manner. As mentioned, the training of a physician usually dictates the management decisions regarding MTP treatment. This study was conducted in a post graduate training institution that has multiple specialty programs with osteopathic recognition. In the single accreditation system, collaborating with allopathic physicians and exposing allopathic residents to osteopathic treatment options was viewed an advancement for patient centered care and osteopathic awareness. As more allopathic physicians expand their skill sets and complete OMT courses, demonstrating the efficacy of a common treatment modality compared to OMT will assist with treatment choice. Comparable efficacy of both options will help patients choose the option that best meets their needs and physicians choose the option that best augments their skill set.

Being a pilot study, we anticipated a considerable degree of limitations throughout the study. Limitations include but are not limited to low sample size, majority female participants, and substantial difference in mean age between the two groups. Additionally, the OMT intervention group had a significantly lower mean pre-intervention pain level compared to the lidocaine group which made it difficult to do a true comparative analysis between groups. However, as a pilot study, demonstration of OMT non-inferiority compared to a standard treatment modality, creates a stepping stone for future research to investigate the comparative efficacy of OMT on a larger scale and we therefore anticipate future trials with larger number of participants to demonstrate more significant data and results.

Conclusion

Based on our study, OMT has comparable value with lidocaine injection technique as a treatment modality for active TrPs in the upper trapezius region. Both techniques demonstrate considerable decrease in pain intensity from baseline and thus it allows for increased collaboration between osteopathic and allopathic practitioners to promote patient centered care.

References

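### Age and treatment group are almost completely confounded (20–29 y: 21 of 21 OMM v 1 of 10 lidocaine), so the SAP's only age-adjusted model cannot give a usable group effect

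*SAP*

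**What the plan says.** The SAP (Data Analysis) lists t-tests within and between groups, then a multivariate analysis by "multiple logistic regression models with age, sex, and intervention group (Injection = 0, OMM = 1) factored as the independent variables". It does not say whether age enters in years or in bands, or what the binary outcome is. The only outcome measure it defines is pain, "measured using a point system; where 0 = no pain and 10 = maximum pain", with no cut-point. The mixed two-factor ANOVA in the SAP's Results contains group and time but not age. The protocol's Data Analysis plans that ANOVA and mentions no logistic regression.

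The SAP's Results report "10 eligible participants from the lidocaine treatment group and 21 eligible participants from the OMM treatment group", and that "1 subject from the lidocaine treatment group was lost during follow-up at one week post intervention and thus excluded from the per protocol analysis". The age of the lost patient is not given. The same section states that the groups did not differ significantly on sociodemographic data, while the Discussion lists as a limitation the "substantial difference in mean age between the two groups". No estimate from the logistic model is reported anywhere.

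**The concern.** A regression can adjust for age only where both groups have patients of similar age. Table 1 shows almost no such overlap, so the model has little with which to tell an age effect from a treatment effect.

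A reader who learns that age was an independent variable in a multivariate analysis may take the between-group comparison as protected against the age gap. The SAP discloses the gap but not that the listed adjustment cannot deal with it. It then concludes that the two treatments have comparable value and refers to non-inferiority. Those statements have no age-adjusted support.

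**Working it through.** **Inputs (SAP, Results, Table 1)**

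| Age band | OMM | Lidocaine | Total (% of 31) |
|---|---|---|---|
| 20–29 | 21 | 1 | 22 (71.0) |
| 30–39 | 0 | 1 | 1 (3.2) |
| over 60 | 0 | 8 | 8 (25.8) |

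The percentages match the SAP's. The bands add to 31, so nobody falls between them.

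**1. Strength of the confounding.** With margins fixed, the observed table has probability C(22,1)·C(1,1)·C(8,8)/C(31,10) = 22/44,352,165 = 5.0 × 10⁻⁷. Every other possible table is more probable, so this is also the exact p-value.

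**2. Age in the Table 1 bands, binary outcome.** The model has five columns: intercept, group, sex and two band indicators. The 30–39 and over-60 bands hold only lidocaine patients, so their band terms absorb everything those patients say about level. The group term is then the contrast, in the 20–29 band, of 21 OMM patients with one lidocaine patient. That one patient has in effect a private intercept and an outcome of 0 or 1, so the maximum-likelihood fit drives it to plus or minus infinity, and the group log odds ratio with it. This follows from the counts. A separation check by linear programming agreed in all simulated data sets (300 at each assumed event rate of 0.3, 0.5 and 0.7). If the lost patient was the one aged 20–29, the design has rank 4 of 5 and group is aliased with age.

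**3. Age in years: variance inflation.** The documents do not give individual ages, so I assume band centres of 27 (25–29, given the SAP's lower limit of 25), 34.5 and 63 (61–65). Ignoring sex, variance inflation for group = 1 + SSB/SSW, where SSB and SSW are the between- and within-group sums of squares of age.

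- All 31: lidocaine mean age (27 + 34.5 + 8 × 63)/10 = 56.55. SSB = (21 × 10/31) × 29.55² = 5,915. SSW = 29.55² + 22.05² + 8 × 6.45² = 1,692. Inflation = 4.5.
- An over-60 patient lost: 1 + 5,238/1,646 = 4.2.
- The 30–39 patient lost: 1 + 6,451/1,152 = 6.6.
- The 20–29 patient lost: 1 + 6,792/722 = 10.4.

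Simulation with sex in the model and ages uniform within bands gives medians of 4.4–4.5, 4.1–4.2, 6.5–6.6 and 10.1–10.2. By √4.5 and √10.1, the standard error is about 2.1 to 3.2 times larger than without age, on a linear-model approximation.

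**4. Age in years: the logistic model itself.** With all 31 patients the simulated group effect was infinite in only 0.3–4% of data sets. Where finite, the median standard error of the log odds ratio was about 2.0 to 3.2. The unadjusted value is √[(1/21 + 1/10)/(p(1−p))] = 0.77 at p = 0.5 and 0.84 at p = 0.3 or 0.7. The 95% limits therefore lie about exp(1.96 × 2.04) = 54-fold to exp(1.96 × 3.16) = 490-fold either side of the odds ratio. If one of the two younger lidocaine patients was lost, the median standard error is 5.0 to 6.8.

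**The case against.** The strongest reply is that the SAP never says age is banded; the bands appear only in a descriptive table. With age in years the model usually converges to a finite estimate, and high variance inflation is imprecision, not failure to estimate. The SAP reports no result from this model, rests no conclusion on it, and already discloses the age gap. All of that is correct, and it rules out several stronger readings that a reader might infer:

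- *That the age-adjusted effect cannot be estimated at all.* This holds only for banded age with a binary outcome, or for banded age if the 20–29 lidocaine patient was lost. The SAP states neither condition.
- *That the estimate is pure extrapolation.* The lidocaine group spans 20–29 to over 60, so it covers the OMM band. The line is interpolated over an empty gap and rests on two younger patients. It becomes extrapolation only if the youngest was lost, which is unknown.
- *That the outcome type is irrelevant.* A linear model of 0–10 pain with banded age on all 31 patients has full rank. Ignoring sex, its group standard error is √(1 + 1/21) = 1.02 residual SDs, against √(1/21 + 1/10) = 0.38 without age. That is finite, though it hangs on one patient.
- *That the loss can be put in pain points from a pooled SD.* The reported t values imply very unequal SDs of one-week change, about 1.63 (OMM) and 4.15 (lidocaine, taking 9 pairs). An unequal-variance calculation gives an unadjusted half-width of about 3.2 points before age is considered. I make no claim in points for the adjusted model.

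What does not stand is that disclosing the age difference is enough. A limitation that names the gap does not tell the reader that the listed adjustment cannot close it.

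**Conclusion.** The point holds in limited form. The one model that contains age gives no usable group effect under either coding: infinite or aliased with bands and a binary outcome; finite but very imprecise, and dependent on an uncheckable straight line, with age in years.

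The counts, the exact p-value and the banded result come from Table 1 alone. The sizes for age in years assume ages uniform within bands up to 65, event rates of 0.3 to 0.7, the two male lidocaine patients placed at random, and no true effects. Raising the oldest age to 75, the upper limit in the protocol's Study Design, leaves variance inflation at about 4.3–4.5 with all patients and about 9–10 if the youngest lidocaine patient was lost.

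The documents do not show that any reported figure came from this model, or that it was meant to answer the age gap. The consequence is for what may be claimed: the between-group results are unadjusted for age. Separately, the Results statement of no significant sociodemographic difference is contradicted by Table 1 for age and is at odds with the Discussion.

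**What to change.** - **SAP, Data Analysis:** stop presenting the logistic model as an adjusted between-group comparison. Say that age and group cannot be reliably separated in these data, give the counts by band, and state that all reported between-group figures are unadjusted for age.
- **If the model as run is reported:** label it a sensitivity analysis and give the coding of age, the binary outcome and its cut-point, the confidence interval, the variance inflation, and the absence of patients aged 40–60. Do not delete age from the description, since the SAP says that the analysis was done.
- **SAP, Results:** correct the statement on sociodemographic balance so that it agrees with Table 1 for age.
- **SAP, Discussion and Conclusion:** repeat the statement beside the age limitation, and qualify the comparability and non-inferiority wording to say that it has no age-adjusted support.

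This needs no new data. The cost is that the SAP gives up the appearance of an age-adjusted comparison.

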- 1 active/latent MTP in the upper trapezius region

The diagnostic criteria to establish myofascial trigger point is adopted from Travell and Simons³ and include:

1. Presence of palpable taut band in the skeletal muscle
2. Presence of hypersensitive tender spot in the taut band
3. Presence of local twitch response upon stimulation of the taut band
4. Reproduction of referred pain upon palpation
5. Presence of spontaneous referred pain pattern

Exclusion criteria: Subjects that exhibited any of the following criteria were excluded from the study:

- Pregnancy or immunocompromise
- Fever/infection
- Previous history of whiplash injury
- Previous history of cervical surgery, cervical radiculopathy, or myelopathy
- Severe disc or cervical lesion
- Evidence of cognitive deficit
- Degenerative or inflammatory disease of the cervical spine or shoulder, fibromyalgia, or neuromuscular diseases
- Use of medications (anticoagulants, anti-inflammatory etc.) or illicit drug use (1 week prior to treatment or follow up)
- Received treatment for MPS a month before the study recruitment

All eligible participants were screened at their respective clinic with the above criteria. Subjects who agreed to participate in the study provided informed consent. At this time, they were given a demographic survey and pre-intervention survey. This survey included a standard pain intensity evaluation using a 0-10 pain scale and a quality-of-life assessment measured by the neck disability index. After enrollment and pre-intervention assessment, the appropriate intervention was administered to

the patient; patients at the Philadelphia OMM clinic received muscle energy treatment, while patients at the Atlanticare Pain Management clinic received lidocaine with dry needling.

Participants presenting to the PCOM OMM clinic were treated with the muscle energy technique of post isometric relaxation on the symptomatic upper trapezius by a board-certified osteopathic physician. After placing patient in a supine position, the shoulder on the affected side was stabilized with one arm. Using the other arm, the head was sidebent contralaterally and rotated ipsilaterally until the restriction barrier was encountered. This position was then maintained for 10 seconds while a normal respiratory rhythm was maintained. After 10 seconds the position was extended further into the barrier and held for 30 seconds and process repeated.

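### The SAP Results report no significant sociodemographic difference, but Table 1 shows almost complete separation by age (exact p = 5.0 × 10⁻⁷); separately, the three stated age ranges are not reconciled

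*SAP*

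**What the plan says.** The SAP's Data Analysis section defines what was to be compared: "The homogeneity of sociodemographic data (age, sex, comorbid conditions" and the outcome measures, using Fisher and chi-square tests with alpha 0.05. Results then report: "No significant difference was found between the two groups in regard to sociodemographic data (Table 1". Table 1 prints age counts by group, including the row "Subjects > 60y, n = 8 (25.8"%), but the P value cells for sex, age and ethnicity are empty.

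The Discussion lists as limitations a "substantial difference in mean age between the two groups" and, for the OMM group, a "significantly lower mean pre-intervention pain level compared to the lidocaine group". The sentence after the second of these refers to "demonstration of OMT non-inferiority compared to a standard treatment modality". Elsewhere the Discussion speaks of equal efficacy, and the Conclusion of comparable value.

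Allocation was by site: "patients at the Philadelphia OMM clinic received muscle energy treatment", and patients at the other clinic received lidocaine with dry needling. For adjustment, Data Analysis names "multiple logistic regression models with age, sex, and intervention group" as the approach.

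On age eligibility, the protocol gives 25–75 in Study Design and 25–60 in Inclusion Criteria. The SAP gives 25–65 in both places, in the past tense.

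**The concern.** In a non-randomised comparison, the statement that the groups do not differ is what a reader relies on before looking at treatment effects. Here it is untrue for age, the covariate with the largest imbalance in Table 1's sociodemographic rows, and it conflicts with the SAP's own Discussion.

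The stakes are higher because nothing in the design or analysis can repair the imbalance. Clinic and treatment are the same variable, so no model fitted to these data can separate them. Age nearly coincides with treatment as well. Baseline pain, the outcome measured before treatment, also differs widely.

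The eligibility question bears on one group in particular. Results describe all 10 lidocaine patients as eligible, but whether most of them were depends on which of three age ranges applied.

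**Working it through.** **1. The plan's own figure.** No p value for age is printed, so only the claim of non-significance at 0.05 can be checked. The Table 1 age counts agree with their percentages: 22/31 = 71.0%, 1/31 = 3.2%, 8/31 = 25.8%. The contradiction is therefore not a garbled table.

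**2. Age, all 31 enrolled.** Counts for 20–29, 30–39 and over 60 are OMM 21, 0, 0 and lidocaine 1, 1, 8. Sidedness is not stated; I use two-sided exact tests.

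- Three bands, margins fixed: C(22,1) × C(1,1) × C(8,8) / C(31,10) = 22 / 44,352,165 = 4.96 × 10⁻⁷. No other table with these margins is as improbable, so this is the exact p.
- 20–29 versus older: the same value, 4.96 × 10⁻⁷.
- Over 60 versus not: C(23,2) / C(31,10) = 253 / 44,352,165 = 5.70 × 10⁻⁶.

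**3. Age, 30 analysed.** One lidocaine patient was lost, age band not given. The denominator becomes C(30,9) = 14,307,150.

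| Band of lost patient | 20–29 versus older | Over 60 versus not |
|---|---|---|
| 20–29 | 1/14,307,150 = 7.0 × 10⁻⁸ | 22/14,307,150 = 1.5 × 10⁻⁶ |
| 30–39 | 22/14,307,150 = 1.5 × 10⁻⁶ | 22/14,307,150 = 1.5 × 10⁻⁶ |
| Over 60 | 22/14,307,150 = 1.5 × 10⁻⁶ | 253/14,307,150 = 1.8 × 10⁻⁵ |

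**4. Size in years.** Taking completed years, the OMM mean is at most 29. The lidocaine mean is at least (20 + 30 + 8 × 61)/10 = 53.8. The means therefore differ by at least 24.8 years.

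**5. Other sociodemographic rows.** Sex (5/21 versus 2/10 male): Fisher p = 1.0. Ethnicity, four categories: exact p = 0.15. The Results sentence fits these two rows, but with 21 and 10 patients non-significance does not show similarity. Caucasian patients make up 90% of the lidocaine group and 52.4% of the OMM group, a gap of 37.6 points (Newcombe 95% CI 2 to 59; Fisher p = 0.055; this collapse is mine). Comorbid conditions, named in Data Analysis, have no row in Table 1.

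**6. Baseline pain (Welch, from summary data).**

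- Lidocaine n = 10, SD 2.87 (Results): SE = √(2.87²/10 + 1.84²/21) = 0.992; t = (7 − 2.76)/0.992 = 4.27, df 12.6, p = 0.001; difference 4.24, 95% CI 2.1 to 6.4.
- Lidocaine n = 9, SD 3.04 (Table 2): SE = √(3.04²/9 + 1.84²/21) = 1.090; t = 3.89, df 10.6, p = 0.003; 95% CI 1.8 to 6.6.

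**7. Can the planned regression adjust for this?** Clinic determines treatment, so clinic cannot be adjusted for. For age, one lidocaine patient shares a band with any OMM patient. If that patient was the one lost, the analysed set has no overlap in bands at all. Results give no output from this regression, and the SAP does not name its dependent variable.

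**8. Age eligibility.**

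| Stated range | Where | What Table 1 shows at the upper limit |
|---|---|---|
| 25–75 | Protocol, Study Design | Cannot be checked: top band is open-ended |
| 25–60 | Protocol, Inclusion Criteria | 8 of 10 lidocaine and 0 of 21 OMM outside |
| 25–65 | SAP, Study Design and Inclusion Criteria | Cannot be checked: top band is open-ended |

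The lower limit of 25 cannot be checked either, because the youngest band starts at 20. That affects 22 of 31 patients, including all 21 OMM patients. The protocol plans enrolment for April to May 2021; the SAP reports November 2021 to February 2022. The protocol's cover date, April 28, 2022, falls after that second window, yet it still carries 25–75 and 25–60.

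**The case against.** The strongest reply is that the Discussion already discloses the problem. It lists the age difference, says the baseline-pain difference made a true comparison difficult, calls the study a pilot and presents its list of limitations as incomplete. Site-based allocation is stated openly in both documents. A reader who goes on to the Discussion is not left with unqualified reassurance.

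That is fair, and it limits the harm. It does not make the Results sentence correct. The Discussion calls the age difference substantial without citing a test or acknowledging the conflict with Results. It does not name clinic as a confounder, and it moves from the baseline-pain caveat straight to non-inferiority. The Conclusion repeats none of the caveats.

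A second reply is that significance tests of baseline balance tell us little. In general I agree, but the SAP chose and reported such a test, and 100% versus 10% in one age band needs no p value.

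A third is that the age range may have been properly amended between the documents. That is possible, given the change of enrolment window. Neither document as provided records or explains a change, and the protocol disagrees with itself in any case. What is established is the inconsistency, not that any patient was a protocol deviation.

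**Conclusion.** The concern holds. The Results sentence is wrong for age under either split examined and whichever patient was lost: exact p runs from 7.0 × 10⁻⁸ to 1.8 × 10⁻⁵ against alpha 0.05, and mean age differs by at least 24.8 years. It is not contradicted for sex or four-category ethnicity. These figures assume two-sided tests and that the Table 1 counts are correct; the bound on mean age also assumes completed years.

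Age, clinic and a 4.24-point difference in baseline pain are all tied to treatment, so these data do not support statements of equal efficacy, comparable value or non-inferiority.

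Separately, the ranges 25–75, 25–60 and 25–65 are unreconciled, and how many of the 10 lidocaine patients were age-eligible cannot be settled from the documents. I take no view on which range is right. These points should be corrected; the evidence for the contradiction is strong.

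**What to change.** 1. Replace the Results sentence with the age counts by group and the exact p value. Give the sex and ethnicity counts with their p values (1.0 and 0.15), without saying the groups are comparable.
2. State in the Discussion and Conclusion that age, baseline pain and clinic are confounded with treatment. Remove or qualify the equal-efficacy, comparable-value and non-inferiority statements.
3. Reconcile the age passages by stating which approved version applied during enrolment. Do not choose a range now that the data are known.
4. Report minimum and maximum age and the number outside each stated range, at both ends, by group. List as deviations only patients outside the version in force.

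The cost is text changes in three SAP sections, one age tabulation if exact ages were recorded, and a check of the approval record. No new data collection is needed.

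### The interaction p = .034 rests on pooled covariances the SAP found unequal (0.115–0.148 without pooling), and the equal-efficacy and non-inferiority claims have no test behind them

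*SAP*

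**What the plan says.** The Protocol (Data Analysis) plans a 2 x 3 mixed ANOVA for each outcome. Its Study Objective mentions non-inferiority but gives no margin. The SAP (Data Analysis) lists independent and paired t-tests and a multiple logistic regression on age, sex and group. The ANOVA appears only in the SAP's Results.

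That paragraph states "As expected, due to small sample size, heterogeneity of covariance matrices was detected" and calls it a limitation. It then says Mauchly's "test of sphericity was examined and found to be significant" (p = .042), applies Greenhouse-Geisser, reports F(1.65, 56) = 3.90, p = .034, and ends: "Due to p-value being less than 0.05, we can confidently reject the null hypothesis and accept the alternative hypothesis".

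Mean baseline pain was 2.76 with OMM and 7.00 with lidocaine (Table 2). Under Outcome Measures the SAP says "we are interested in looking at the difference between pre- and post-intervention pain intensity ratings". The Results also say "No significant difference was found between the two groups in regard to sociodemographic data".

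The Discussion says neither technique was superior, that efficacy was equal, and that non-inferiority of OMT was demonstrated. It concedes the gap in baseline pain, the difficulty this caused for a true comparison, and the difference in mean age.

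**The concern.** - **Pooling.** The ANOVA pools two covariance matrices that the SAP found to differ. When the smaller group has the larger variance, pooling understates the error and the test rejects too often. This is the only between-group test of pain in the Results text.
- **Conclusions without a test.** A significant interaction says the two time courses differ, which sits badly with equal efficacy. A non-significant one would not show equality or non-inferiority either. Each needs a margin and a test, and there is neither.
- **Baseline.** No reported analysis conditions on baseline pain, although the means are 4.24 points apart on a 0–10 scale.
- **Loose ends.** The logistic model has predictors but no binary outcome or cut-point, and no result is reported. Table 1 prints 0.026 and 0.062 on the post-intervention pain rows without saying there what they test.

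At stake is whether the trial's comparative conclusions have any inferential support.

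**Working it through.** **1. Rebuild the data summaries.** Assumption: scores are whole numbers from 0 to 10, so sums, squares and cross-products are integers. Table 2 then implies:

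| | Sums (pre, immediate, week) | Sums of squares | SDs |
|---|---|---|---|
| OMM, n = 21 | 58, 39, 38 | 228, 91, 150 | 1.841, 0.964, 2.015 |
| Lidocaine, n = 9 | 63, 59, 36 | 515, 435, 182 | 3.041, 2.455, 2.179 |

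The printed SDs fit if truncated (2.0154 as 2.01, 2.4552 as 2.45, 2.1794 as 2.17).

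The within-group t values in Results give the SD of change = mean change × √n / t:
- OMM immediate: 0.905 × √21 / 2.10 = 1.97
- OMM one week: 0.952 × √21 / 2.68 = 1.63
- Lidocaine one week: 3.00 × √9 / 2.16 = 4.17 (4.15 at the nearest integer cross-product, t = 2.167)
- Lidocaine immediate: the n = 10 means (7.00, 6.60) imply that the excluded patient scored 70 − 63 = 7 and 66 − 59 = 7. With t = 1.177 on n = 10, the SD for the nine completers is 1.13.

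These are paired tests, although Results calls them independent-samples tests. Independent-samples formulas would give t = 2.00 and 1.60 (OMM) and 2.41 (lidocaine, one week), against the printed 2.10, 2.68 and 2.16. The lidocaine tests are printed with 20 df, but their p values fit 8–9 df.

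**2. Reproduce the SAP's figure.** The group differences in means (lidocaine minus OMM) are d = (4.238, 4.698, 2.190). Let P be the centring matrix, so d′Pd = 3.565. The combined immediate-by-week cross-product must be 297, which gives a pooled tr(PSₚ) = 5.764. Then

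F = [(21 × 9)/30] × 3.565 / 5.764 = 3.896, df 1.654 and 46.3, p = .0345, Mauchly p = .0421.

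The SAP reports 3.90, 1.65, .034 and .042. Its printed error df of 56 is uncorrected. A cross-product of 296 gives F = 3.88 and 298 gives 3.91. Only the split of 297 between the groups is unknown, and 29 splits keep both covariance matrices admissible.

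**3. Remove the pooling.** Use V = S₁/21 + S₂/9 and the ANOVA-type statistic d′Pd / tr(PV). The df are f₁ = tr(PV)² / tr((PV)²) and f₂ = tr(PV)² / {[tr(PS₁)/21]²/20 + [tr(PS₂)/9]²/8}.

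| Split | tr(PS₁) OMM | tr(PS₂) lidocaine | tr(PV) | Statistic | df | p |
|---|---|---|---|---|---|---|
| One end | 4.295 | 9.435 | 1.253 | 2.845 | 1.22, 11.3 | 0.115 |
| Middle | 3.829 | 10.602 | 1.360 | 2.621 | 1.25, 10.6 | 0.131 |
| Other end | 3.362 | 11.769 | 1.468 | 2.429 | 1.25, 10.0 | 0.148 |

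Pooling replaces tr(PV) by 5.764 × (1/21 + 1/9) = 0.915, against 1.25–1.47 without it.

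Multivariate tests with group-specific covariances give 0.076–0.249 (Krishnamoorthy-Yu) and 0.063–0.264 (Yao). If the reported ANOVA output is ignored as a constraint, 1,682 pairs of covariance matrices are admissible, and the three tests span 0.109–0.154, 0.029–0.287 and 0.021–0.293.

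**4. False rejection at nominal 5%** (normal data, 40,000 runs for each of 29 splits): Greenhouse-Geisser 11.6–14.8%, ANOVA-type 4.8–5.4%. Allowing for uncertainty in the estimated covariances, the Greenhouse-Geisser rate has a median of 12–15% (5th–95th percentile 5–20%).

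**5. Group contrasts, OMM minus lidocaine (95% CI).** None depends on the unknown split.

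| | Immediate | One week |
|---|---|---|
| Raw, Welch | −4.70 (−6.61 to −2.79) | −2.19 (−4.01 to −0.37), p = 0.022 |
| Change, Welch | −0.46 (−1.64 to 0.72), p = 0.43 | +2.05 (−1.18 to 5.28), p = 0.19 |
| Baseline-adjusted, common slope | −2.90 (−4.25 to −1.54) | −1.14 (−3.36 to 1.08), p = 0.30 |
| Separate slopes, at baseline 2.76 | −1.49 (−2.81 to −0.18) | −2.94 (−6.14 to 0.27) |
| Separate slopes, at baseline 7 | −4.43 (−5.72 to −3.14) | +0.81 (−1.58 to 3.21) |

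The adjusted values partly extrapolate: 7 is (7 − 2.76)/1.84 = 2.3 SD above the OMM mean, and 2.76 is (7 − 2.76)/3.04 = 1.4 SD below the lidocaine mean.

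**6. Table 1.** The one-week 0.062 equals the lidocaine within-group p in Results. Between groups at one week the p values are 0.013 (raw, pooled), 0.022 (raw, Welch), 0.059 (change, pooled) and 0.19 (change, Welch). Immediate pain between groups gives p < 0.001 raw and 0.37–0.52 on change, so 0.026 matches none of them. Age 20–29 is 21/21 against 1/10: Fisher p = 5 × 10⁻⁷.

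**The case against.** The mixed ANOVA was the protocol's planned analysis, the SAP discloses the heterogeneity, and the Discussion claims no superiority. On that view, toning down one adverb and adding a sensitivity test would be enough. Several narrower points are fair:

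- The variance imbalance is not uniform. For immediate change the lidocaine SD is the smaller (1.13 against 1.97). The simulation uses the full matrices, however, and the net effect is still liberal. The largest component of the interaction, immediate to one week, is 2.51 points with Welch p = 0.054–0.111.
- The common-slope intervals themselves pool residual variance. Allowing unequal variances moves the estimates to about −0.1 (SE 1.3) at one week and −3.7 (SE 0.8) immediately.
- SAP Data Analysis loosely assigns a chi-square test to homogeneity of the outcome measures. That cannot be rebuilt from means and SDs, so it cannot be excluded as the source of 0.026. A misprint of the lidocaine within-group 0.27 is also possible.
- The Discussion does admit the age imbalance, although Results denies a sociodemographic difference.
- Simulations on normal data only approximate bounded scores near the floor.

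These points stand as qualifications. None restores p = .034, and none supplies a margin or a test for equality or non-inferiority. Disclosing a violation that more than doubles the false-rejection rate does not justify confidence in the rejection.

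**Conclusion.** The concern holds and must be fixed. With group-specific covariances the interaction is not significant under any of the three tests for any reconstruction that fits the reported output. The ANOVA-type p is 0.115–0.148. Without that constraint the multivariate tests can fall below 0.05, but the ANOVA-type test cannot.

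At one week even the direction of the group difference depends on the method. Immediately after treatment every method favours OMM, but size and significance vary. Neither result can be attributed to treatment, because site is fully, and age almost fully, confounded with group. Equal efficacy and non-inferiority are untested.

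The decimals rest on whole-number scores, truncated SDs and reading the within-group tests as paired. The direction is secure, and the held data will give exact values.

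**What to change.** 1. Re-run the interaction and the change contrasts on the held data with methods that allow group-specific covariances: Welch/Satterthwaite, ANOVA-type, or a mixed model with a separate unstructured covariance per group.
2. Keep the raw and change-score results. Beside them, report as a sensitivity analysis a baseline-adjusted linear model with unequal residual variances and a group-by-baseline term, and state the limited baseline overlap. With nine lidocaine patients this can only be supportive.
3. Label all of this as post hoc.
4. Record that the logistic model was stated without an outcome and not reported, and do not rely on it.
5. Explain or correct 0.026 and 0.062 in Table 1, and correct the Results statement on sociodemographic similarity.
6. Remove the claims of confident rejection, equal efficacy and demonstrated non-inferiority. State that the one-week comparison is inconclusive, that the immediate difference depends on the method, and that neither can be attributed to treatment.

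The cost is wording and a re-run; no new data are needed. The interaction p becomes less favourable. The one-week 95% CI widens from 3.4 points (raw, pooled) to 4.4 (common slope), 4.8–6.4 (separate slopes) or 6.5 (change, Welch). Confounding by site and age is not removed and must remain a stated limit.
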